 [name] (Jun 27, 2023 07:13 GMT+3) [name] (SCM, trial PI)

 Jun 27, 2023
 [name] (Jun 27, 2023 23:06 GMT+3) [name] (SCM, BDI committee co-chair)

[figure not shown]
 Jun 27, 2023
 [name] (Jun 27, 2023 10:56 GMT+3) [name] (SCM, BDI committee chair)

*SCM = Steering Committee Member of the FINISH trial

4. Blinded data interpretation (BDI)

The data will be interpreted according to a blinded data interpretation scheme we have published and described in detail previously [9]. In brief, the FINISH statistician (TC) will carry out the statistical analyses, blinded to the group assignment, and presents the data as Group A and Group B. The FINISH Blinded Data Interpretation committee will then contemplate the blinded results until a consensus on the interpretation is reached. Once the Blinded Data Interpretation committee reaches a consensus, the data will be unblinded and no changes are made to the interpretation of the results.

The sequence of events to take place in the upcoming ‘blinded data interpretation meeting’ is outlined in the flow chart below:

The final BDI plan was approved by:

Jun 27, 2023
[name] (Jun 27, 2023 07:13 GMT+3)
[name] (trial PI)

Jun 27, 2023
[name] (Jun 27, 2023 00:01 GMT+3)
[name] (local PI, SCM)

Jun 27, 2023
[name] (Jun 27, 2023 08:43 GMT+3)
[name] (local PI, SCM)

Jun 28, 2023
[name] (Jun 28, 2023 15:02 GMT+3)
[name] (local PI, SCM)

Jun 27, 2023
[name] (Jun 27, 2023 08:33 GMT+3)
[name] (local PI, SCM)

Jun 27, 2023
[name] (Jun 27, 2023 08:21 GMT+3)
[name] (local PI, SCM)

Jun 27, 2023
[name] (Jun 27, 2023 14:13 GMT+3)
[name] (SCM)

Jun 27, 2023
[name] (Jun 27, 2023 07:55 GMT+3)
[name] (SCM)

Jun 28, 2023
[name] (Jun 28, 2023 10:49 GMT+2)
[name] (trial statistician)

Jun 27, 2023
[name] (Jun 27, 2023 18:40 GMT+2)
[name] (BDI committee member)

Jun 27, 2023
[name] (Jun 27, 2023 09:55 GMT+3)
[name] (SCM, BDI committee member)

Jun 27, 2023
[name] (Jun 27, 2023 23:06 GMT+3)
[name] (SCM, BDI committee co-chair)

Jun 27, 2023
[name] (Jun 27, 2023 10:56 GMT+3)
[name] (SCM, BDI committee chair)

*SCM = Steering Committee Member of the FINISH trial

Minutes of the BDI**[BLINDED VALUES TO BE ADDED BY TRIAL STATISTICIAN PRIOR TO THE BDI MEETING]****Step 1: Analysis of efficacy (primary, non-inferiority analysis)**

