As we will not have knowledge of treatment group assignment (whether Group A or Group B is our “new treatment”, here, no irrigation), and to preserve our blinding, we have deemed it necessary to take both scenarios under consideration, as follows:

[figure not shown]
- We will calculate the treatment group difference assuming first that Group A is the “new treatment” and then that Group B is the “new treatment” (Scenario 1 and Scenario 2).
- We will plot the resulting point estimate with confidence intervals (97.5% CIs) into two separate graphs.
- We will interpret both graphs (Figures 2 and 3).

Figure 2. Scenario 1 – Group A minus Group B.

[EXAMPLE GRAPH BELOW, to be replaced by the actual graph of the FINISH trial data]

**Figure 3.** Scenario 2 – Group B minus Group A.

[EXAMPLE GRAPH BELOW, to be replaced by the actual graph of the FINISH trial data]

Step 2: Initial interpretation of efficacy

Based on the location of the whole CI in relation to Δ (non-inferiority margin), our initial interpretation on the non-inferiority of no irrigation vs. irrigation, is as follows:

Scenario 1 (Figure 2) [INCORRECT OPTION TO BE REMOVED]

1. Among adults with symptomatic chronic subdural hematoma who had undergone burr-hole drainage, Group A was [superior A / non-inferior B, C, D / inferior H] to Group B in preventing reoperations.

OR

2. Among adults with symptomatic chronic subdural hematoma who had undergone burr-hole drainage, the effect of Group A compared to Group B in preventing reoperations was inconclusive [E, F, G].

Scenario 2 (Figure 3) [INCORRECT OPTION TO BE REMOVED]

3. Among adults with symptomatic chronic subdural hematoma who had undergone burr-hole drainage, Group B was [superior A / non-inferior B, C, D / inferior H] to Group A in preventing reoperations.

OR

4. Among adults with symptomatic chronic subdural hematoma who had undergone burr-hole drainage, the effect of Group A compared to Group B in preventing reoperations was inconclusive [E, F, G].

Step 3: Analysis of safety concerns

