Given that the objective of surgery for CSDH extends beyond preventing reoperations to also encompass the improvement of neurological function and prevention of death, the entire treatment effect of intraoperative irrigation (versus no irrigation) may not be adequately captured by focusing solely on the primary outcome measure, the rate of reoperations. We deemed it crucial to also consider the potential impact of between-group differences in deaths and/or unfavorable functional outcomes, as both could have an effect on the rate of reoperations. We felt that in the name of transparency and trustworthiness, we would need to define *a priori* thresholds for between-group differences in mortality and rate of unfavorable functional outcome (mRS 4–6) at 6-months that we consider “concerning” or “alarming”.

We considered a difference to be “concerning” if the 85% confidence interval (CI) of the absolute between-group difference in mortality or rates of unfavorable functional outcome (mRS 4–6) did not encompass the value of 0.0 and “alarming” if the 95% CI of the absolute between-group difference in mortality or mRS 4–6 rates did not encompass the value of 0.0.

Prior to establishing the thresholds for the 85% CI (“concerning”) and 95% CI (“alarming”) thresholds, we conducted simulations to ensure that these thresholds would yield clinically relevant differences in mortality and unfavorable functional outcome (mRS 4–6) (Figure 4). For the mortality simulations, we assumed a mortality rate of 5% in the standard care group. This selection was based on two recent similar-sized RCTs, in similar settings (Sweden [11], UK [12]), where the 6-month mortality rate was 5% in the groups treated with burr-hole craniostomy and subdural drainage. As for the mRS 4–6 simulations, we assumed an mRS 4–6 rate of 10% based on the results of the DEX-CSDH [12] and DESCA trials [13].

[figure not shown]

Figure 4. Simulation of the 95% (left panel) and 85% (right panel) confidence intervals for between-group differences in 6-month mortality rates (upper panel) and rates of mRS 4–6 (lower panel). The difference in mortality and/or rates of mRS 4–6 is significant if the 85% CI or 95% CI does not encompass the value of 0.0.

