Acknowledging that the FINISH trial was not powered for assessing differences in mortality or rate of unfavorable functional outcome (mRS 4–6), we used a 3-level hierarchy (**low** / **moderate** / **high**) for expressing our confidence in the possible between-group differences according to the GRADE approach [14–16]. We assumed a 6-month mortality rate of 5% [12,17] and an mRS 4–6 rate of 10% [12]. In terms of **mortality**, the confidence in the estimate was considered **low** if the overall 6-month mortality rate was **<5%**, **moderate** if the overall 6-month mortality rate was **5–10%**, and **high** if the overall 6-month mortality rate was **>10%**. Regarding 6-month unfavorable functional outcome (**mRS 4–6**), the confidence in the estimate was considered **low** if the rate of mRS 4–6 was **<10%**, **moderate** if the rate of mRS 4–6 was **10–15%**, and **high** if the rate of mRS 4–6 was **>15%**.

Our scheme for interpreting the possible safety concerns is outlined in Tables 3 and 4.

Table 3. A priori set thresholds for **concerning** and **alarming** between-group differences in 6-month mortality with associated confidence estimates and pre-determined commitments for interpretation.

Overall mortality in whole population	Confidence in estimate	Threshold for relevant between-group difference in mortality	Resulting action if threshold fulfilled	Authors' interpretation commitment
<5%	Low	Concerning: The 85% confidence interval of the between-group difference in absolute mortality-% does not include 0.0	None	We refrain from making any comments due to the low event rate (low confidence in effect estimate).
		Alarming: The 95% confidence interval of the between-group difference in absolute mortality-% does not include 0.0	Notion on safety concern added to the discussion (not added to the conclusion).	Group A/B was associated with an alarmingly higher mortality rate. Given the event rate, the confidence in this finding was low .
5–10%	Moderate	Concerning: The 85% confidence interval of the between-group difference in absolute mortality-% does not include 0.0	Notion on safety concern added to the discussion (not added to the conclusion).	Group A/B was associated with a concerningly higher mortality rate. Given the event rate, the confidence in this finding was moderate .

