		Alarming: The 95% confidence interval of the between-group difference in absolute mRS 4–6 rate does not include 0.0	Notion on safety concern added to the conclusion.	Group A/B was associated with an alarmingly higher rate of unfavorable functional outcome. Given the event rate, the confidence in this finding was moderate .
>15%	High	Concerning: The 85% confidence interval of the between-group difference in absolute mRS 4–6 rate does not include 0.0	Notion on safety concern added to the conclusion.	Group A/B was associated with a concerningly higher rate of unfavorable functional outcome. Given the event rate, the confidence in this finding was high .
		Alarming: The 95% confidence interval of the between-group difference in absolute mRS 4–6 rate does not include 0.0	Notion on safety concern added to the conclusion.	Group A/B was associated with an alarmingly higher rate of unfavorable functional outcome. Given the event rate, the confidence in this finding was high .

Table 5. Safety concerns for the intention-to-treat dataset.

Variable	All patients (n=??)	Group A (n=??)	Group B (n=??)	Difference (95% CI)	Difference (85% CI)	P-value
6 mo mortality	??/n (??%)	??/n (??%)	??/n (??%)	x (x to x)	x (x to x)	??
6 mo mRS 4–6	??/n (??%)	??/n (??%)	??/n (??%)	x (x to x)	x (x to x)	??

Abbreviations: mRS=modified Ranking Scale, CI=confidence interval

Table 6. Safety concerns for the per-protocol dataset.

Variable	All patients (n=??)	Group A (n=??)	Group B (n=??)	Difference (95% CI)	Difference (85% CI)	P-value
6 mo mortality	??/n (??%)	??/n (??%)	??/n (??%)	x (x to x)	x (x to x)	??
6 mo mRS 4–6	??/n (??%)	??/n (??%)	??/n (??%)	x (x to x)	x (x to x)	??

Abbreviations: mRS=modified Ranking Scale, CI=confidence interval

Imbalance in the incidence of safety concerns (mortality and/or mRS 4–6)?

NO / YES [INCORRECT OPTION TO BE REMOVED]

If NO, the following sentence will be added to the conclusion: “There were no relevant differences in mortality or functional outcome between the groups.”

If YES, interpretation according to **Table 3** (mortality) and **Table 4** (unfavorable functional outcome)

Step 4: Unblinding of treatment groups

Having now considered both the rate of reoperations and safety concerns, we have now reached a consensus on our blinded assessment of efficacy.

Our statistician will now unblind the treatment group assignment (break the randomization code):

- Group A = Irrigation / No irrigation [**INCORRECT OPTION TO BE REMOVED**]

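### The fixed conclusion sentence reports failure to detect a difference in deaths or poor function as absence of a relevant difference, in a trial not powered for either outcome

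*SAP*

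**What the plan says.** Section 4 (BDI), Step 3, calls a difference concerning "if the 85% confidence interval (CI) of the absolute between-group difference in mortality" or in mRS 4–6 leaves out 0, and alarming if the 95% CI does. Tables 3 and 4 head these two rules as the thresholds for a relevant between-group difference. The Figure 4 caption says that a difference "is significant if the 85% CI or 95% CI does not encompass the value of 0.0". Simulations were run "to ensure that these thresholds would yield clinically relevant differences in mortality and unfavorable functional outcome"; their output is in Figure 4, which is not visible in the text at hand.

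Step 3 introduces its confidence grading with "Acknowledging that the FINISH trial was not powered for assessing differences in mortality or rate of unfavorable functional outcome (mRS 4–6". The low, moderate or high grade then depends on the overall event rate, and Tables 3 and 4 attach it only to results that cross a threshold.

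Step 3 ends with a NO/YES question on imbalance. "If NO, the following sentence will be added to the conclusion": "There were no relevant differences in mortality or functional outcome between the groups". Step 5 repeats that sentence in the 'No difference' row under each of the four primary results. After consensus the data are unblinded and "no changes are made to the interpretation of the results".

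For the primary outcome, Step 2 has a third category, in which "the effect of Group A compared to Group B in preventing reoperations was inconclusive". The safety column of Step 5 has only two entries, difference or no difference.

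Section 3.2 allows treatment non-inferiority to be claimed only if (1) reoperation is non-inferior in both ITT and PP, and (2) there is no relevant difference in mortality or mRS 4–6, judged by the BDI approach.

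**The concern.** An interval that includes 0 shows that a difference was not detected. It shows that no relevant difference exists only if the interval also excludes every difference that would matter, and the visible text names no such difference for deaths or mRS 4–6. The same plan sets a 7.5-point margin and an inconclusive category for reoperation.

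The grading is also one-sided. With overall mortality below 5%, an 85% flag leads to no comment because confidence is low. At the same low event rate, an unflagged result gets an unqualified reassurance.

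At stake is a locked line in the trial's conclusion. Readers could be told that deaths and function did not differ relevantly when the data remain compatible with clearly more deaths in one group.

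**Working it through.** **Inputs.** Final sample size 289 per group (SAP 2.9.2). Assumed rates of 5% mortality and 10% mRS 4–6 (Section 4, Step 3). Flag rule: 85% or 95% CI of the absolute difference excludes 0. The SAP does not name the interval method, so Wald is an assumption: d ± z·√[p₁(1−p₁)/n + p₂(1−p₂)/n], with z = 1.4395 (85%) and 1.9600 (95%). The SAP gives 587 or 588 randomized, about 294 per group; this barely changes the results.

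**The plan's own figure.** For reoperation: (1.960 + 0.842)² × 2 × 0.096 × 0.904 / 0.075² = 242.2, so 243 per group or 486 in total. 486/0.90 = 540 and 486/0.843 = 576.5, rounded in the SAP to 578. These reproduce. The SAP gives no power figure for mortality or mRS 4–6.

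**Largest unflagged excess near the assumed rates.**

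| Counts (289 per group) | Difference, points | 85% CI | 95% CI | 85% flag |
|---|---|---|---|---|
| Deaths 22 v 14 (7.6% v 4.8%) | 2.77 | -0.12 to 5.66 | -1.17 to 6.70 | no |
| Deaths 23 v 14 | 3.11 | 0.19 to 6.04 | | yes |
| mRS 4–6, 40 v 29 (13.8% v 10.0%) | 3.81 | -0.07 to 7.68 | -1.47 to 9.08 | no |
| mRS 4–6, 41 v 29 | 4.15 | 0.25 to 8.05 | | yes |

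For 22 v 14: √[0.0761 × 0.9239/289 + 0.0484 × 0.9516/289] = 0.0201. Then 1.4395 × 0.0201 = 2.89 points and 1.9600 × 0.0201 = 3.93 points either side of 2.77.

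**How often the sentence is printed.** Simulation of one ITT look, with deaths counted within mRS 4–6 and mRS 4–5 at 5% in both groups. NO is taken to mean no 85% flag on either outcome.

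| True mortality | True mRS 4–6 | Sentence printed |
|---|---|---|
| 5% v 5% | 10% v 10% | 76% |
| 5% v 7.5% | 10% v 12.5% | 50% |
| 5% v 8% | 10% v 13% | 42% |
| 5% v 10% | 10% v 15% | 16% |

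The first row is the rule working as intended. Among trials that print the sentence at 5% v 7.5%, the median upper 95% limit for the mortality difference is +5.1 points, about the size of the whole assumed death rate. If NO instead meant no 95% flag, the sentence would be printed more often: 71% rather than 50% in the second row.

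**Sensitivity of the rule.** The 85% rule flags mortality of 5% v 10% in 81% of trials on mortality alone, against 64% with the 95% rule. The smallest true difference flagged with 80% power is about 5.0 points for mortality and 6.4 points for mRS 4–6.

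**Which analysis set decides.** Tables 5 (ITT) and 6 (PP) both report the flags, and Step 3 does not say which governs. If PP is taken as a random 84.3% of patients (1 − 0.157), the two sets give different NO/YES answers in about 13% of trials with no true difference and 15% at 5% v 7.5% with 10% v 12.5%. Randomness is an assumption; SAP 2.9.2 shows that non-adherence was mostly short drainage or no drain.

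**Claim rule against Step 5.** Section 3.2 makes absence of a relevant difference a condition of the treatment claim. In Step 5, the 'Non-inferior' with 'Difference' row still prints non-inferiority in preventing reoperations, and adds a safety statement only where Tables 3 and 4 send it to the conclusion. Nothing in that row shows condition 2 taking effect.

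**The case against.** The best defence is that relevant is a defined term. The table headers tie it to the 85% and 95% rules, simulations are cited in support, and so the sentence only reports that no threshold was crossed. That is a fair reading within the plan, and because Figure 4 is not visible one can say only that the visible text sets no tolerable difference. But the simulations are described as showing which differences get flagged; no text says that an unflagged result rules out a relevant one. A reader of the conclusion will take the word in its ordinary sense.

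The 85% level is a deliberate allowance for low power, and it buys real sensitivity. Tables 5 and 6 give both intervals and are copied into the unblinded minutes, and nothing bars printing a caveat beside the sentence. These points reduce the harm, but the locked sentence itself still carries no interval, grade or caveat.

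Two stronger inferences are not supported. A reader might infer that the plan conceals the uncertainty; it does not, since the intervals are tabulated and the lack of power is stated. A reader might also infer that Section 3.2 and Step 5 contradict each other outright. Section 3.2 restricts a claim of treatment non-inferiority and defers to the BDI, while Step 5 prints the narrower statement about reoperations. The two can coexist; what is missing is wording that links them.

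**Conclusion.** The point stands as a defect of wording in the fixed conclusion. Followed as written, the plan prints non-detection as absence of a relevant difference. Excesses of 2.8 points in mortality and 3.8 points in mRS 4–6, with upper 95% limits of 6.7 and 9.1 points, would be reported that way. So would about half of trials with a true excess of 2.5 points in both outcomes, and about 42% with a true excess of 3 points.

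This rests on Wald intervals, 289 per group, the SAP's assumed rates, and reading NO as no 85% flag, which is inferred from the definitions and table headers. The alternative reading (no 95% flag) makes the problem larger. The link between condition 2 and Step 5 is a secondary matter of reconciliation. The primary test and the flag thresholds are not called into question.

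**What to change.** **Main change.** In Steps 3 and 5, replace the sentence with: *Mortality was x% v y% (difference z, 95% CI a to b) and mRS 4–6 was x% v y% (difference z, 95% CI a to b). No pre-set threshold was crossed; the trial was not powered to exclude differences in these outcomes.* The cost is a longer, less reassuring conclusion that partly repeats Tables 5 and 6. No analysis or threshold changes.

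**Clarify.** Define NO, say whether Table 5 or Table 6 decides it, and say whether a concerning result in the lowest event-rate tier counts as YES.

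**Reconcile.** Make condition 2 of Section 3.2 and the Step 5 row 'Non-inferior' with 'Difference' agree; how is for the sponsor to choose. One option is wording in that row that the reoperation criterion was met but treatment non-inferiority is not claimed, stating which flags trigger this and what happens in the lowest tiers. With no true difference, and assuming flags are independent of reoperation, withholding on any two-sided 85% flag would lose the claim in about 24% of otherwise non-inferior trials. Withholding only on flags against no irrigation would lose about 12%, and only on two-sided 95% flags about 8%. Section 3.2 itself says deaths and poor function may affect reoperation, so these figures are approximate. The other option is to amend condition 2 to match Step 5, which avoids that cost but weakens the stated safeguard.

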3.2 Final statistical analysis plan

The primary outcome for efficacy is the rate of symptomatic CSDH ipsilateral recurrences requiring reoperation within 6 months. The statistical analysis for efficacy will be performed according to both the ITT and PP principles. The ITT analysis will be performed using the full analysis set, defined as all randomized patients in the groups allocated by randomization. No exclusions other than those caused by missing information will be made. No imputation will take place. The PP analysis will be performed on the subset of the full analysis set that is compliant with the protocol, has completed treatment, has available measurements, and has no major protocol violations or entry criteria violations.

As the goal of CSDH surgery is not only to prevent reoperations but also to improve neurological function and prevent death, the entire therapeutic effect (value) of intraoperative irrigation (versus no irrigation) may not be sufficiently comprehensively captured by analysing the primary outcome (rate of reoperations) only. For example, any possible between-group differences in the incidences of deaths and unfavorable functional outcomes may have an effect on the likelihood of a patient being considered for reoperation (i.e., skew the primary analysis).

Prompted by this realization, we deemed it necessary to somehow take into account between-group differences in either mortality and/or unfavorable functional outcome (mRS 0–3 vs. 4–6) in interpreting the findings of the FINISH trial. The approach, to be used in the blinded data interpretation (BDI) [8] of the FINISH trial, is outlined below. In addition, in the event that we will observe a statistically significant difference in the number of deaths

between the two groups, we will carry out a detailed analysis of the causes of death by examining the official death certificates of the participants.

We will claim treatment non-inferiority only if:

- 1) Our primary efficacy analysis, based on the primary outcome, shows non-inferiority and the finding is supported both by the ITT and the PP analyses,
and
- 2) there are no relevant between-group differences in mortality (alive or dead at 6 months) or unfavorable functional outcome (mRS 0–3 vs. 4–6 at 6 months) between the groups (according to an approach outlined in the BDI).

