Summary statistics will be presented for both groups. Continuous variables will be presented in terms of mean values or medians with SDs and IQRs, respectively. Categorical variables will be presented with relative frequencies in percent.

The results from the statistical analysis will be considered to support a claim of non-inferiority if the upper limit of a one-sided 97.5% CI (or equivalently a 95% two-sided CI) excludes a difference in the primary endpoint in favor of the irrigation group of more than 7.5%. The center stratification of the randomization will be accounted for in the calculation of the CI.

Exploratory analyses of secondary and other binary endpoints will be performed using the χ^2 test or logistic regression analysis. Continuous outcomes will be analyzed using regression Student's t-test, analysis of covariance or regression models.

Potential effect modifiers will be analyzed by including interaction terms in statistical models for the following subgroups:

- patient age (<70 years, \geq 70 years)
- GCS score at baseline (9–12, 13–14, 15)
- history of head trauma (<4 weeks, \geq 4 weeks, head trauma with unknown timing, no head trauma)
- unilateral versus bilateral CSDH
- use of anticoagulation and/or antiplatelet medication versus none
- preoperative mRS (0–3, 4–5)
- hematoma density (isodense, mixed-density, hypodense)
- hematoma size (width in mm)
- presence of membranes on preoperative imaging (yes, no)

The primary endpoint will be investigated as described above using a CI, which is equivalent to using a non-inferiority test with a one-sided p-value of 0.025 (or a two-sided of 0.05). The between-group comparison of 6-month mortality and mRS 4–6 differences will be compared using 85% and 95% CIs (as outlined in more detail in the BDI). The statistical testing of other endpoints will also be performed using a two-sided significance level of 0.05.

STATA (Statistics/Data analysis, SE v15.1, StataCorp LLC, [name]) will be used for analyses.

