- Group B = Irrigation / No irrigation [**INCORRECT OPTION TO BE REMOVED**]

Given the above noted, the FINISH data is shown in **Table 1**, **Table 2**, **Table 5 and Table 6** (with n-values for Groups to be added) and in Scenario 1 (**Figure 2**) or Scenario 2 (**Figure 3**). [**INCORRECT OPTION TO BE REMOVED**]. The rate of crossovers is reported here:

- Crossovers from Group A to B, n=?? [**INSERT DATA**]
- Crossovers from Group B to A, n=?? [**INSERT DATA**]

[**COPY TABLE 1 HERE AND INSERT DATA**]

[**COPY TABLE 2 HERE AND INSERT DATA**]

[**COPY TABLE 5 HERE AND INSERT DATA**]

[**COPY TABLE 6 HERE AND INSERT DATA**]

[**COPY FIGURE 2 OR FIGURE 3 HERE**]

Step 5: Unblinded interpretation of treatment effect

Accordingly, our penultimate interpretation of the FINISH trial is as follows:

[CORRECT OPTION TO BE CHOSEN]

Treatment comparison	Primary outcome results	Interpretation based on primary outcome	Between-group difference in safety concerns (mortality, mRS 4-6)	Interpretation commitment regarding safety concerns (mortality, mRS 4-6)
No intraoperative irrigation vs. intraoperative irrigation	Non-inferior	Among adults with symptomatic chronic subdural hematoma who had undergone burr-hole drainage, no intraoperative irrigation was noninferior to intraoperative irrigation in preventing reoperations.	No difference	There were no relevant differences in mortality or functional outcome between the groups.
			Difference	“Interpretation commitment” from Tables 3 and 4 added if criteria for addition to conclusion is fulfilled.
	Superior	Among adults with symptomatic chronic subdural hematoma who had undergone burr-hole drainage, no intraoperative irrigation was superior to intraoperative irrigation in preventing reoperations. However, be it noted that we did not design the study to show superiority.	No difference	There were no relevant differences in mortality or functional outcome between the groups.
			Difference	“Interpretation commitment” from Tables 3 and 4 added if criteria for addition to conclusion is fulfilled.
	Inferior	Among adults with symptomatic chronic subdural hematoma who had undergone burr-hole drainage, no intraoperative irrigation was inferior to intraoperative irrigation in preventing reoperations. However, be it noted that we did not design the study to show inferiority.	No difference	There were no relevant differences in mortality or functional outcome between the groups.

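### Step 5 can conclude superiority in a trial that section 3.2 bars from claiming non-inferiority, and no analysis set is named for the superiority label

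*SAP*

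**What the plan says.** Section 3.2 of the SAP holds the only claim rule. It opens "We will claim treatment non-inferiority only if" and lists two conditions. The first is that the primary analysis "shows non-inferiority and the finding is supported both by the ITT and the PP analyses". The second is that "there are no relevant between-group differences in mortality (alive or dead at 6 months) or unfavorable functional outcome". The criterion in the same section is that the "upper limit of a one-sided 97.5% CI (or equivalently a 95% two-sided CI) excludes a difference in the primary endpoint" of more than 7.5% in favour of irrigation. Superiority does not appear in 3.2.

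It first appears in section 4, Step 2, where the committee may record that "Group A was [superior A / non-inferior B, C, D / inferior H] to Group B in preventing reoperations". The basis is given as "Based on the location of the whole CI in relation to Δ (non-inferiority margin), our initial interpretation on the non-inferiority", and the plotting instruction is "We will plot the resulting point estimate with confidence intervals (97.5% CIs) into two separate graphs". Table 2 reports an ITT and a PP interval, but each scenario has one graph with one point estimate, and no analysis set is named for it.

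Step 5 then supplies the final wording. In the Superior row it is that "no intraoperative irrigation was superior to intraoperative irrigation in preventing reoperations", with a note that the study was not designed to show this. The row has two sub-rows, for no difference and for a difference in mortality or mRS 4–6. In the second, the superiority sentence stays, and a safety sentence from Tables 3 and 4 is added only if those tables send it to the conclusion.

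**The concern.** Superiority on reoperations implies non-inferiority on reoperations, so the stronger claim should meet at least the conditions of the weaker one. Here two conditions are stated for the weaker claim and neither is carried over.

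The safety condition matters most. Section 3.2 explains it by noting that deaths or poor functional outcome can change a patient's chance of being considered for reoperation. That reasoning applies with equal force to an apparent reduction in reoperations: an excess of deaths without irrigation could itself produce one.

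The analysis set matters second. For non-inferiority, 3.2 says how ITT and PP combine. For superiority the committee would have to decide this after seeing both intervals. Section 4 fixes the interpretation once the groups are unblinded, so the rule has to be complete before then.

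**Working it through.** **The plan's own figure.** Section 2.9.1: 9.6% in both groups, margin 7.5%, one-sided alpha 0.025, power 80%.

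n = (1.960 + 0.842)² × 2 × 0.096 × 0.904 / 0.075² = 242.2, so 243 per group. Then 243 / 0.90 = 270. Section 2.9.2: 486 / (1 − 0.157) = 576.5, taken to 578, or 289 per group. All are reproduced.

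**The rules side by side.**

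| | Section 3.2 | Step 5, Non-inferior row | Step 5, Superior row |
|---|---|---|---|
| Analysis set | ITT and PP must agree | not restated | not stated anywhere |
| Relevant safety difference | claim withheld | claim kept, text may be added | claim kept, text may be added |

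For non-inferiority, 3.2 and Step 5 conflict, but a rule exists. For superiority only Step 5 exists.

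**Simulation inputs.** 289 per group; 9.6% reoperation with irrigation; PP a random 84.3% of each group (0.843 × 289 ≈ 244); mortality 5% and mRS 4–6 10% including deaths (the rates assumed in section 4, Step 3), equal in both groups and independent of reoperation; safety read on ITT. Interval: d ± z√[p₁(1−p₁)/n₁ + p₀(1−p₀)/n₀], with d = no irrigation minus irrigation. Centre stratification is ignored. Runs: 200,000 to 400,000 per scenario. Superiority is taken as an upper limit below 0.

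**1. Confidence-interval criterion.** An upper limit below 0 is also below 7.5%. No simulated trial that was superior in either set failed the margin in ITT or PP. With equal true rates, ITT superiority occurs in 2.6% of trials, against 78.8% for non-inferiority in both sets (60.1% once the 85% safety condition is added). Condition 1 is therefore not bypassed in practice.

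Hand check at a true rate of 6.0%: SE = √[(0.0564 + 0.0868)/289] = 0.0223; 0.036/0.0223 = 1.62; Φ(1.62 − 1.96) ≈ 0.37. The simulation gives 36.7%.

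**2. Safety condition.** With no true difference, at least one of the two intervals excludes 0 in about 24% of trials at 85% and 8% at 95%. If the two outcomes were independent, nominal levels would give 1 − 0.85² = 27.8% and 1 − 0.95² = 9.8%; overlap between them lowers this. About half the exclusions point to harm from no irrigation.

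Trials superior in ITT with the 85% condition failed:

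| True rate, no irrigation | ITT superior | and condition 2 failed | share |
|---|---|---|---|
| 9.6% | 2.6% | 0.6% | 24% |
| 6.0% | 36.7% | 8.7% | 8.7/36.7 = 24% |
| 4.6% | 66.2% | 15.6% | 15.6/66.2 = 24% |

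**3. Analysis set.** With 95% CIs:

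| True difference (points) | ITT superior | PP-only superior |
|---|---|---|
| 0 | 2.5% | 0.98% |
| −3 | 26% | 3.6% |
| −4 | 45% | 3.8% |
| −5 | 66% | 3.1% |

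If either set sufficed, the error under equal rates would be 2.5 + 0.98 ≈ 3.5%. If the 97.5% intervals of Table 2 and the graphs are two-sided, it is 1.8%. (The 2.5% here and the 2.6% in step 1 come from separate simulations of the same quantity.)

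**The case against.** A reader might infer that superiority is the easier claim, or that no condition attaches to it. The documents do not support either. The label needs interval class A, carries a caveat about design, and has the same safety columns as the other rows. Under the plan's assumptions it is much the harder claim to reach. Only at very large effects does superiority without the safety condition become more likely than non-inferiority with it (92.3% against 76.4% at a true rate of 3.0%).

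A reader might also infer that the plan lets either analysis set carry the claim. It does not say so: both analyses are run and shown to the committee, and the plan is silent on how they combine for superiority. The 3.5% is the cost of one reading of that silence, and it falls below 2.5% if the plotted intervals are two-sided 97.5%. The figure defining classes A to H and the flow chart are not shown in the available text, so class A as an interval wholly below 0 is an assumption.

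It can further be argued that a superiority claim contains a non-inferiority claim, so 3.2 already reaches it. That is a sensible reading, but Step 5 contradicts it with a ready sentence for superiority alongside a safety difference.

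The remaining objections stand. The safety mismatch also affects the Non-inferior row. Condition 2 is written without direction, so about half its chance failures would favour no irrigation. At the assumed event rates, a difference at the 85% threshold leads under Tables 3 and 4 only to a note in the discussion.

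**Conclusion.** The point holds for the safety condition and the analysis set, and not for the interval criterion. A trial in which 3.2 withholds non-inferiority because mortality or mRS 4–6 differ can be concluded as superior under Step 5, and nothing says which set's interval decides that label.

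The size depends on which threshold counts as relevant, which 3.2 does not settle: about 24% of ITT-superior trials at 85% or 8% at 95% would be affected by chance alone, about half of that in the direction of harm. PP-only superiority is smaller, about 1% of trials with no effect and 3–4% at a true 3–5 point benefit. These figures rest on random PP exclusions and on safety outcomes independent of reoperation. The documents do not show which way departures from these assumptions would move the figures.

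Superiority is not the trial's hypothesis, but Step 5 is a stated rule that gives an incoherent conclusion if followed. It should be corrected before unblinding.

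**What to change.** Add to section 3.2 and to the Superior row of Step 5: superiority will be claimed only if both conditions of 3.2 for non-inferiority are met and the ITT two-sided 95% CI of the difference lies wholly below 0; the PP interval is supportive. Testing in this order costs no alpha.

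Reconcile the Difference sub-rows of both the Non-inferior and Superior rows with condition 2 by writing the conclusion used when it fails: report the reoperation difference and the safety difference, with no claim of non-inferiority or superiority. No such wording exists in the plan now. State at the same place which threshold (85% or 95%) and which direction make a difference relevant.

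The cost is a few sentences and no new data or analyses. There will be fewer superiority claims: those resting on PP alone, and those with condition 2 unmet. The latter are up to about 24% of ITT-superior trials at the 85% threshold or 8% at 95%, and about half that if condition 2 is read only in the direction of harm.
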